In IRB-HSR# 8588, the normal girls in early puberty (Tanner stages 1-3, n=4) had increased hypothalamic progesterone sensitivity compared to their older counterparts (Tanner stages 4-5, n=16) (percent reduction in LH pulses after 7 days of estradiol and progesterone 86.5% in Tanner 1-3 vs. 54.1% in Tanner 4-5). Although only a small number of Tanner 1-3 subjects were studied and the results do not achieve statistical significance, the finding is quite intriguing. Free testosterone concentrations rise 4- to 8-fold during the course of female puberty ([name] et al, 2007). As androgens mediate reduced hypothalamic progesterone sensitivity in adult women with PCOS, we hypothesize that the gradual increase in free testosterone across the course of female puberty may lead to a gradual reduction in hypothalamic progesterone sensitivity.

In this study, we propose to investigate this hypothesis by assessing the relationship between hypothalamic progesterone sensitivity and androgen levels in normal puberty. We will measure hypothalamic progesterone sensitivity and androgen levels in normal girls in early to mid puberty (Tanner 1-3). These results will be compared to historic data in normal controls in late puberty (Tanner 4-5) that were collected as part of IRB-HSR# 8588.

A better understanding of neuroendocrine function during pubertal maturation may lead to insights regarding abnormal pubertal maturation (e.g. precocious puberty) or disorders with pubertal onset (e.g. PCOS). Hopefully this research will translate into improved prevention and treatment for these disorders in the future.

In addition to the main portion of the study, we will be measuring a variety of cytokines and adipokines in these subjects. This is part of a larger project to try to understand the origins of adolescent hyperandrogenemia and the extent to which cytokines and adipokines may play a role in increasing testosterone production in preadolescent and adolescent girls. These girls will be a source of normal control data for this exploratory project.

Brief Summary: Please see the abstract on page 5.

Additional Information

A. Investigators Experience

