Type of specimen to be used: Blood Please list the information and identifiers that will be with the specimen when it is given to you. Name, medical record #, GCRC protocol #, time (date and clock hour) drawn. If you are using discarded tissue do you confirm that it will be obtained either from pathology, a clinical lab or the UVa Tissue Procurement Facility? Not applicable. Will you be using viable embryos? No Will you be using embryonic stem cells? No Do you plan to ship any specimens outside of UVA? No Will the specimen be obtained before a subject has signed a consent form? No

Study Design: Biomedical

What kind of controls will be used? Only normal control subjects will be studied.Single-blind, double-blind, other: This study is not blinded.If randomized, how? This study is not randomized.Does the study involve a placebo? No

Bio-statistical Analysis

Explain bio-statistical analysis to be done:

Sample Size Determination. If a total of 10 normal tanner-stage 1-3 girls complete both CRU admissions, and the true group to group difference in the percentage change in LH pulse frequency following estradiol and progesterone supplementation is greater than or equal to 30%, we anticipate that we will have at least an 80% chance of rejecting the null hypothesis that estradiol and progesterone supplementation alters LH pulse frequency to the same degree in both normal tanner-stage 1-3 and normal tanner-stage 4-5 girls. This effect size was determine based on the following set of assumptions: (a) the percentage change in LH pulses frequency following estradiol and progesterone supplementation is normally distributed in both study populations, (b) the within-subject measurement variability (standard deviation) in the percentage change LH pulse frequency will not exceed 26.6% in either group (standard deviation based on the data from IRB-HSR# 8588), (c) the two-sided type I error rate of the statistical test will not exceed 0.05, and (d) the power of the statistical test will be at least 0.80.

Base on our previous protocol (IRB-HSR# 8588), we anticipated that the subject dropout rate will not exceed 35% in this study population. Therefore, we intend to enroll 16 normal tanner-stage 1-3 girls into this study.

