Statistical Analyses: We will analyze the LH pulse frequency data from the tanner stage 1-3 normal girls and the LH pulse frequency data from the tanner stage 4-5 normal girls, by way of a linear-mixed effects ANCOVA model. The response variable will identify the change in the LH pulse frequency between the LH pulse frequency measured at the first overnight admission (baseline) and that measured at the second overnight admission (after progesterone supplementation). The ANCOVA model will include one independent factor and two independent continuous covariates. The independent factor will identify the girl's tanner stage (1-3, or

Assessment of the sensitivity of the hypothalamic GnRH pulse generator to estradiol and progesterone inhibition in early pubertal girls (JCM026)

4-5), while the two independent continuous covariates will identify the girl's progesterone levels at baseline and following estradiol and progesterone supplementation. Based on the parameter estimates from the ANCOVA model, we will be able to compare the magnitude of the change in LH pulse frequency after estradiol and progesterone supplementation between the two groups of girls after adjusting for the girls' progesterone concentration following estradiol and progesterone supplementation (overnight admission 1) and after adjusting for the girls' progesterone concentration following estradiol and progesterone supplementation (overnight admission 2). A generalized-F-test will be utilized to formally test the null hypothesis that estradiol and progesterone supplementation alters LH pulse frequency in tanner-stage 1-3 girls to the same degree as in normal tanner-stage 4-5 girls. The decision rule to reject the null hypothesis, will be based on a P≤0.05 criterion. Confidence interval construction, for estimating the true group to group difference in the percentage change in LH pulse frequency after estradiol and progesterone supplementation, will be base on the Students t-distribution multiplier. The PROC MIXED procedure of SAS version 9.1.3 EAS (SAS Institute Inc, Cary NC) will be used to conduct the aforementioned statistical analyses.

In order to ensure an adequate sampling of younger girls, no more than 4 enrolled subjects will be Tanner stage 3. The number of subjects in each Tanner stage will be reported with the final results.

What is the primary outcome variable upon which a sample size estimate is based?

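### The claim of at least 80% power names no control number; with the 16 historic girls cited in the background, the planned t/F-type test has about 76%

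*Combined protocol and SAP*

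**What the plan says.** Under Bio-statistical Analysis, Sample Size Determination, the combined protocol and SAP states that with 10 Tanner 1-3 girls completing both admissions and a true group difference of 30% or more in the percentage change of LH pulse frequency, "we anticipate that we will have at least an 80% chance of rejecting the null hypothesis". The listed assumptions are normality in both groups, a two-sided type I error of 0.05, power of at least 0.80, and a standard deviation that "in the percentage change LH pulse frequency will not exceed 26.6% in either group", taken from IRB-HSR# 8588. The list contains no number of controls and no power formula.

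The comparator is identified in the background: the new results will be "compared to historic data in normal controls in late puberty (Tanner 4-5) that were collected as part of IRB-HSR# 8588". The same section gives the only count for that group when it describes the earlier findings in Tanner 1-3 girls "compared to their older counterparts (Tanner stages 4-5, n=16").

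The Statistical Analyses paragraph specifies the test. "The ANCOVA model will include one independent factor and two independent continuous covariates": Tanner group, and progesterone at baseline and after supplementation. "A generalized-F-test will be utilized to formally test the null hypothesis", and the confidence interval for the group difference "will be base on the Students t-distribution multiplier".

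**The concern.** Two-sample power depends on both group sizes. The paragraph gives one of them, so its power figure cannot be reproduced from its own contents. When the missing number is filled in with the only candidate in the document, the stated 80% appears under the normal approximation but not under the kind of test that the analysis section plans. With 26 girls the two differ by more than rounding, and the claim is worded as a minimum.

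What is at stake is how a null result would be read. If the controls number 16, the chance of missing a true 30-point difference is about 23 to 24% before any covariate effect, where the plan promises at most 20%. Without the control number a reader cannot tell whether the stated power applies.

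**Working it through.** **Inputs**

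| Quantity | Value | Source |
|---|---|---|
| Tanner 1-3 completers | 10 | Sample Size Determination |
| Tanner 4-5 controls | 16 (assumed to be the analysis set) | Background |
| Difference in percentage change | 30 points | Sample Size Determination |
| SD, each group | 26.6 points | Sample Size Determination |
| Type I error | 0.05, two-sided | Sample Size Determination |
| Model terms | one factor, two covariates | Statistical Analyses |

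**Step 1: reproduce the plan's figure.** The standard error of the group difference is 26.6 × √(1/10 + 1/16) = 26.6 × √0.1625 = 10.72. The standardised difference is 30 / 10.72 = 2.798. By the normal formula, power = Φ(2.798 − 1.960) = Φ(0.838) = 79.9%. This matches the stated 80% after rounding. It suggests, without proving it, that 16 controls and a normal formula were used.

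**Step 2: use the planned type of test.** A 1-df F-test is equivalent to a two-sided t-test, so power comes from the noncentral t distribution with noncentrality 2.798.

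- Group factor only: 10 + 16 − 2 = 24 df, critical value 2.064, power 76.6%. A simulation of 200,000 two-sample t-tests gave 76.5%.
- Group factor and two covariates: 26 − 4 = 22 df, critical value 2.074, power 76.2%. This assumes that the covariates explain no outcome variance and do not differ between groups.

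**Step 3: the difference detectable with 80% power, 10 against 16.** Normal formula: (1.960 + 0.842) × 10.72 = 30.0 points. Noncentral t: 31.3 points (24 df) or 31.4 points (22 df).

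**Step 4: dependence on the control number, with 10 completers.**

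| Controls | t-test, no covariates | Two fewer df |
|---|---|---|
| 16 | 76.6% | 76.2% |
| 17 | 77.6% | 77.3% |
| 18 | 78.6% | 78.3% |
| 19 | 79.5% | 79.2% |
| 20 | 80.3% | 80.0% |

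The background mentions 20 normal girls in all (4 + 16), but 4 of them were Tanner 1-3 and so are not Tanner 4-5 controls.

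**Step 5: effect of the covariates, 10 against 16, 22 df.** The documents give no figure for either direction, so these are illustrations.

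- Covariates balanced between groups and explaining a share R² of outcome variance raise the noncentrality to 2.798 / √(1 − R²). Power reaches 80% at R² = 0.089.
- Covariates explaining no outcome variance but sharing 10% of their variance with Tanner group lower the noncentrality to 2.798 × √0.9 = 2.654. Power falls to 71.8%.

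**The case against.** The strongest reply is that what has been demonstrated is an omission, not a wrong number. Nowhere does the plan say that 16 is the comparator set; that count describes an earlier comparison. With 20 usable controls the claim is true. This stands as a condition on the 76% figure. It also shows why the number has to be stated, since the truth of the claim turns on it.

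A second reply is that the gap is a matter of formula and is small beside the uncertainty of the inputs. An SD of 25.5 instead of 26.6 restores 80% at 24 df. The earlier study's own difference, 86.5 − 54.1 = 32.4 points, gives 82.6%. If 26.6 had been estimated on 15 df (an assumption), its 95% interval would run from about 19.6 to 41.2, and power at 24 df from about 95% down to 41%. All this is correct, and the shortfall is modest. It does not rescue the statement, because the plan sets 30 points and 26.6 as its own limits and promises at least 80% at those limits.

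A third reply is that 76% is not the power of the planned ANCOVA either, because the covariates may raise or lower it. That also stands. The sample-size paragraph claims no gain from adjustment, so any restated figure should carry its covariate assumption.

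Finally, a null result would be read mainly from the planned Student-t interval and the actual group sizes. That limits the consequence, but it does not make the power statement correct.

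**Conclusion.** The concern holds. The paragraph omits the control number and the formula. With the only count that the document offers, the promised minimum is met only, after rounding, by the normal approximation (79.9%). The planned t/F-type test has 76.6% (24 df) or 76.2% (22 df), which is 3.4 to 3.8 points short, or 1.3 to 1.4 points on the detectable difference.

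This rests on four assumptions: 16 is the analysis set; 26.6 is the between-girl SD of the percentage change, although the plan labels it as within-subject measurement variability; the test is made on the percentage-change scale, although the analysis section says "The response variable will identify the change in the LH pulse frequency"; and the covariates have no net effect. Confidence is medium, mainly because of the first. The correction should be made, but the design does not depend on it.

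**What to change.** In Sample Size Determination:

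- State how many historic Tanner 4-5 girls will be analysed and which power formula was used.
- If the number is 16, restate the claim as about 76% power for a 30-point difference, or 80% power for about 31.3 to 31.4 points, and say that no covariate effect is assumed.
- If 20 or more usable historic controls exist, give that number; the 80% claim can then stay.
- If 80% with 16 controls relies on covariate adjustment, state the outcome variance assumed to be explained. About 9% is needed, with the groups balanced on progesterone.
- State that 26.6% is the between-girl SD of the percentage change, if that is so, and which subjects it came from.

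The cost is one or two sentences. No extra enrolment and no change to the analysis are needed.

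### The stated power of at least 80% is about 77% by the planned t/F test, and the SD behind it carries the wrong label

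*Combined protocol and SAP*

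**What the plan says.** Under Bio-statistical Analysis, Sample Size Determination, the protocol considers 10 Tanner 1-3 girls completing both admissions. It takes 30% as the threshold, supposing that "the true group to group difference in the percentage change in LH pulse frequency following estradiol and progesterone supplementation is greater than or equal to" this figure, and says "we anticipate that we will have at least an 80% chance of rejecting the null hypothesis" of equal change in the two Tanner groups.

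The listed assumptions include:

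- (b), on the SD: "the within-subject measurement variability (standard deviation) in the percentage change LH pulse frequency will not exceed 26.6% in either group", with the source given as "standard deviation based on the data from IRB-HSR# 8588"
- (c), on the error rate: "the two-sided type I error rate of the statistical test will not exceed 0.05"
- (d), on the target: "the power of the statistical test will be at least 0.80"

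Assumption (a) is normality in both groups. The section gives neither the number of historic controls nor the power formula. It does not say which girls in the earlier study supplied the SD.

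Statistical Analyses, in the same part, plans an ANCOVA with one factor (Tanner 1-3 or 4-5) and two progesterone covariates. The group effect is tested by a generalized F-test, and the confidence interval uses a Student's t multiplier.

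The Background reports the pilot from IRB-HSR# 8588: percent reductions of "86.5% in Tanner 1-3 vs. 54.1% in Tanner 4-5", with 4 and 16 girls. It adds that "the results do not achieve statistical significance", and names no test, SD or P value.

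**The concern.** There are two problems, of unequal weight.

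First, the promised power does not match the planned test. The analysis uses t and F distributions with few degrees of freedom, where a normal approximation overstates power. The calculation has to be done on the basis that the analysis will use.

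Second, assumption (b) names a quantity that does not fit the design. Each girl contributes one change between two admissions, and separate groups of girls are compared. The variance that matters is the spread of percentage change across girls. Measurement variability within a girl is only one component of that spread, so a reader cannot tell from the text whether the wording or the input is wrong.

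The pilot gives a partial check on the number, because it comes from the study that supplied the SD.

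At stake is how a non-significant result is read. This calculation is the only justification given for 10 completers.

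**Working it through.** **Inputs**

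- Difference 30, read as percentage points; two-sided alpha 0.05; SD 26.6; 10 new completers (Sample Size Determination).
- 16 Tanner 4-5 controls (Background; the sample size section does not restate the number).
- Pilot: 86.5% with n = 4 and 54.1% with n = 16, a difference of 32.4 points (Background).

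**1. Reproducing the plan's figure.** Treat 26.6 as the SD between girls.

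- SE = 26.6 × √(1/10 + 1/16) = 26.6 × 0.4031 = 10.72
- 30/10.72 = 2.798
- Normal approximation: power = Φ(2.798 − 1.960) = Φ(0.838) = 79.9%

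This agrees with the stated 80% to rounding, which suggests that 26.6 was used as a between-girl SD and 16 as the control number.

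**2. Power on the basis of the planned test.** Use the noncentral t with noncentrality 2.798.

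| Basis | df | Critical value | Power |
|---|---|---|---|
| Normal approximation | – | 1.960 | 79.9% |
| Two-sample t | 10 + 16 − 2 = 24 | 2.064 | 76.6% |
| t less two covariate df | 22 | 2.074 | 76.2% |

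Solving the 24-df calculation for 80% power gives a detectable difference of 31.3 points. With the difference held at 30, 11 completers give 79.0% and 12 give 81.1%.

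**3. The pilot as a check on the SD.** Take SD 26.6 in both groups.

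- Pooled t: SE = 26.6 × √(1/4 + 1/16) = 14.87; t = 32.4/14.87 = 2.18 on 18 df; p = 0.043.
- Welch: the same t = 2.18, but df = (26.6²/4 + 26.6²/16)² / [(26.6²/4)²/3 + (26.6²/16)²/15] = 4.6; p = 0.086.

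The reported non-significance is therefore in tension with SD 26.6 under a pooled t-test and consistent with it under Welch. For the pooled test to be non-significant, the SD must be at least 32.4/(2.101 × 0.559) = 27.6. At 27.6, power for 30 points with 10 against 16 is 73.5% (24 df).

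**The case against.** The best defence is that 26.6 is the right number under a loose label. Assumption (b) describes it as an SD of percentage change. A girl with two admissions has only one such value, so the earlier study's before-and-after data give no within-girl SD of that quantity. Step 1 supports this reading, and it stands.

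A reader might infer more: that a within-subject SD was put into the formula, and that this is why 80% is not reached. The documents do not support that. The shortfall in step 2 is present with 26.6 taken as the between-girl SD, and it comes from using the normal distribution where the plan uses t.

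A reader might also infer that the pilot proves 26.6 too small. It does not. The test is not named, and with four girls in one group Welch or a rank test would be a natural choice. Even under a pooled t-test the gap is one point of SD, 27.6 against 26.6. An SD left over after covariate adjustment could also be slightly below the raw one, and the documents do not exclude that. Nor do they give any upper bound for the SD, so much lower power at some larger assumed SD is not a finding about this plan.

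It is also fair to say that the shortfall is about 3 points and that the planned confidence interval would show the precision of a null result. Both are true and limit the consequences. They do not make the statement of at least 80% correct; even the normal approximation falls just short of it.

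**Conclusion.** The point holds in a limited form. Under the plan's own inputs and planned test, power for a 30-point difference is 76.6%, or 76.2% after two covariate degrees of freedom. Power of 80% applies to a difference of 31.3 points.

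This rests on 16 controls, on reading 30% as percentage points, and on a common SD of 26.6 between girls. It makes no allowance for precision gained or lost through the progesterone covariates beyond their degrees of freedom.

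The within-subject label in assumption (b) is wrong for this comparison, most likely as wording. The pilot is a reason to verify the SD and no more. If the pilot test was a pooled t, the SD is at least 27.6 and power is at most about 73.5%. If it was Welch, there is no conflict.

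**What to change.** In Sample Size Determination:

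- Relabel assumption (b) as the SD of percentage change between girls.
- Confirm 26.6 from the IRB-HSR# 8588 records. Say which girls it comes from and how many, and give it by Tanner group if the data allow.
- State that the comparison uses 16 historic Tanner 4-5 girls.
- Restate power from the t distribution: about 77% for 30 points, or 80% for 31.3 points. Update both figures if the confirmed SD differs from 26.6.

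In the Background, name the pilot test and give its P value. That would settle whether the pilot and the SD agree.

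The cost is a wording change and a recalculation from data already held. The downside is that the stated power becomes slightly less favourable. No extra participants are needed.

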The oral micronized progesterone suspension formulated by the University of Virginia Investigational Drug Pharmacy has been used in several other IRB-HSR approved protocols. We have administered the progesterone suspension to at least 37 adolescent girls and at least 11 adult women.

Oral estrogens, in various formulations, have been used to treat millions of women, although exact numbers are unknown.

• If this protocol will be used in minors please describe any previous use of this drug with minors of a similar age range.

The oral micronized progesterone suspension formulated by the University of Virginia Investigational Drug Pharmacy has been given to 37 adolescent girls as part of our protocols, 4 of whom were Tanner 1-3 pubertal stage. All of these subjects were also given estrace. There have been no adverse effects.

Although Estrace is not often prescribed to adolescent girls, there is significant experience with estrogens in the older adolescent population, generally in the form of oral contraceptive pills. Oral contraceptive pills have been shown safe and effective in adolescent girls, and are commonly used for a number of medical conditions, including hyperandrogenism, as well as for contraception. However, oral contraceptive pills are generally not prescribed to the girls in early adolescence (Tanner 1-3 pubertal stage) that we will be studying in this protocol.

Hypothesis to be Tested:

We hypothesize that the sensitivity of the GnRH pulse generator to suppression by estradiol and progesterone decreases during the course of normal female puberty coincident with a rise in androgen levels. Specifically, we hypothesize that the Tanner 1-3 normal subjects in this study will have a 30% greater reduction in LH(GnRH) pulse frequency after 7 days of estradiol and progesterone than historic Tanner 4-5 normal controls.

ABSTRACT

Women with PCOS have decreased GnRH pulse generator sensitivity to suppression by estradiol and progesterone, as do hyperandrogenic adolescent girls. In adult women, hypothalamic progesterone insensitivity appears to be androgen mediated as sensitivity can be restored with the use of the androgen receptor blocker

Page 4 of 24 Version Date: 2-29-12

Assessment of the sensitivity of the hypothalamic GnRH pulse generator to estradiol and progesterone inhibition in early pubertal girls (JCM026)

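### The primary test is written on change in LH pulse frequency, with no baseline-frequency term, but the hypothesis, power and confidence interval are on percentage change

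*Combined protocol and SAP*

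**What the plan says.** The Statistical Analyses paragraph of Bio-statistical Analysis defines the tested outcome: "The response variable will identify the change in the LH pulse frequency between the LH pulse frequency measured at the first overnight admission (baseline" and the frequency at the second admission. It then lists the whole model: "The ANCOVA model will include one independent factor and two independent continuous covariates". The factor is Tanner group, "while the two independent continuous covariates will identify the girl's progesterone levels at baseline and following estradiol and progesterone supplementation". Baseline LH pulse frequency does not appear.

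Other parts of the plan use a different scale:

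- **Prior data** (Background): "percent reduction in LH pulses after 7 days of estradiol and progesterone 86.5% in Tanner 1-3 vs. 54.1% in Tanner 4-5".
- **Hypothesis to be Tested**: the new girls "will have a 30% greater reduction in LH(GnRH) pulse frequency after 7 days of estradiol and progesterone than historic Tanner 4-5 normal controls".
- **Sample Size Determination**: the effect to be detected is that the "group to group difference in the percentage change in LH pulse frequency following estradiol and progesterone supplementation is greater than or equal to 30" percent. The normality assumption and the SD of 26.6% are also stated for percentage change.
- **Confidence interval**, in the same paragraph as the response definition: it is "for estimating the true group to group difference in the percentage change in LH pulse frequency after estradiol and progesterone supplementation".

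Study Design states: "This study is not randomized". The comparison group is historic.

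**The concern.** On its plain reading, the response is a subtraction of one frequency from another, although the word absolute is not used. Nowhere do the documents say that change means percentage change.

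The two scales ask different questions when the groups start from different frequencies. A girl's drop in frequency is her baseline multiplied by her fractional reduction. A test on the drop, without baseline in the model, therefore mixes hypothalamic sensitivity with starting frequency. The groups differ in pubertal stage by design, and the Abstract describes gonadotropin levels rising through puberty, so equal baselines cannot be taken for granted.

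Three things are at stake: whether the stated power applies to the test that will be run, whether a baseline difference can hide or imitate the hypothesised effect, and whether the planned interval can come from the fitted model. An undefined scale also leaves room to choose it after the data are seen, in an unblinded study whose control data already exist.

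**Working it through.** **Inputs from the documents.** Ten Tanner 1-3 completers; effect 30 points; SD 26.6; two-sided 0.05; power at least 80% (Sample Size Determination). Prior reductions 86.5% and 54.1%, a difference of 32.4 points; 16 Tanner 4-5 girls (Background). The sample-size paragraph gives no control number, so using 16 there is an assumption.

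**Step 1: reproduce the stated power.**

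- Standard error = 26.6 × √(1/10 + 1/16) = 26.6 × 0.403 = 10.72.
- 30/10.72 = 2.80, and 2.80 − 1.96 = 0.84, so power is 79.9% by the normal approximation.
- The noncentral t gives 76.6%.

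The stated 80% thus reproduces on the percentage scale. On the change-in-frequency scale it cannot be computed, because the documents give neither baseline frequencies nor an SD for the change.

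**Step 2: break-even, from protocol figures only.** Let r be the Tanner 1-3 mean baseline divided by the Tanner 4-5 mean baseline. With true reductions of 84.1% (54.1 + 30) and 54.1%, the mean drops are equal when r × 84.1 = 54.1, so r = 0.64. With the prior 86.5%, r = 54.1/86.5 = 0.63. Below break-even, the sign of the group difference reverses.

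**Step 3: illustration with assumed baselines.** There were 20,000 simulated trials per cell, 10 girls against 16. Baseline was normal with mean r or 1 and CV 20% to 25% (assumed). Percent reduction was normal with SD 26.6 and independent of baseline. The model had group plus two covariates unrelated to outcome (22 df). Power counts significant results in the hypothesised direction.

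| Baseline ratio r | True 30-point effect: power on change in frequency | Equal suppression (54.1% in both): rejection on change in frequency |
|---|---|---|
| 1.25 | – | 16% to 17%, nearly all imitating the hypothesis |
| 1.0 | 57% to 61% | 5% |
| 0.8 | 17% to 19% | 13%, nearly all opposite to the hypothesis |
| 0.64 | 2% | – |
| 0.5 | 0.1%, plus 15% to 16% significant the wrong way | – |

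A dash marks a cell not tabulated. With a true effect, percentage change has 72% to 73% power throughout. This is below the 76.6% of step 1 because two uninformative covariates are estimated.

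**Step 4: robustness.**

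- *No covariates.* Power on change in frequency is 60% to 66% at r = 1.0, 18% to 19% at 0.8 and 2% at 0.64, against 76% to 77% on percentage change. In a separate run with an assumed Tanner 4-5 mean of 8 pulses and CV 25%, the percentage test rejects in about 5% of trials under equal suppression, whatever the baselines.
- *Integer counts, reductions capped at 100%, no covariates* (same assumed mean and CV, 6,000 trials). Power on change in frequency is 55%, 14% and 1% at r = 1.0, 0.8 and 0.64, against 72% to 73% on percentage change. Under equal suppression, change in frequency rejects in 14% at 0.8 and 16% at 1.25.

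**The case against.** **Change may be shorthand.** The test paragraph repeats the null hypothesis of the sample-size paragraph, then gives the interval on percentage change and assigns everything to one procedure, without signalling two endpoints. On that reading the bias figures describe an analysis nobody intended. This may be so. But the sentence defines the primary test, the null is worded so that it fits either scale, and an analyst following the text would subtract. What is proven is an unreconciled definition, not an intention to use the wrong scale.

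**The harm depends on unknown baselines.** This stands. Only the 0.64 break-even comes from protocol figures. With equal baselines there is no bias, only lost power, and nothing shows that the true ratio is near 0.64 or 0.5.

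**The simulation leans towards percentage change.** This also stands. Drawing reduction independently of baseline favours that scale, and a normal with mean 84.1 and SD 26.6 puts about 27% of Tanner 1-3 girls above 100%. The capped integer-count check shows the same pattern.

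**Baseline frequency could be a covariate instead.** In the uncovaried set-up with an assumed Tanner 4-5 mean of 8, CV 25% and Tanner 1-3 means of 8, 6, 5 and 10, adding baseline to the change model brings null rejection to about 3% to 5%. Power is 73%, 53%, 34% and 66% respectively. This is a legitimate alternative, but the power would have to be redone and the interval redefined.

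**Percentage change is fragile at low counts.** Partly right. If each pulse is retained at random (binomial counts), its power is 53% to 55% at a Tanner 1-3 mean of 4 pulses and 48% to 49% at 2, against 59% to 60% at 8. That model adds count noise on top of the 26.6 SD, so it is pessimistic. It still shows that power at low counts depends on the count model.

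**Conclusion.** The concern holds: the primary response is wrong as written and must be corrected before analysis. Read literally, the F-test is not on the scale on which the trial was hypothesised and powered, omits baseline pulse frequency, and comes from a model that cannot give the planned interval. This rests on the text alone.

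The size of the harm is conditional. The reversal point of 0.64 uses only the plan's figures. The loss of power to 17% to 19% at a ratio of 0.8, and false rejection of 13% at 0.8 and 16% to 17% at 1.25, rest on the assumed baseline ratios, the CV of 20% to 25%, 16 controls, and reduction independent of baseline. If percentage change was always intended, the correction is one of wording, but it is still needed.

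**What to change.** In the Statistical Analyses paragraph:

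- State that the response is the percentage change in LH pulse frequency from admission 1 to admission 2.
- Take both the F-test and the confidence interval from that one model.
- Keep change in frequency as a secondary analysis.
- State in advance how a girl with no baseline pulses is handled. For example, she is not evaluable for percentage change, the number of such girls is reported, and she stays in the secondary analysis.

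The cost is rewording one paragraph, with no new data, participants or visits. The downside is at low counts. If Tanner 1-3 baseline counts were Poisson with mean 4 to 2 (assumed), e⁻⁴ to e⁻² gives 2% to 14% of girls with zero pulses, and the chance of at least one among 10 is 17% to 77%. Unadjusted power after excluding them was about 71% to 72% in that simulation, but it is lower under the binomial count model described above.

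If the investigators prefer change in frequency as primary, the plan needs baseline frequency as a covariate, a new power calculation on that scale and a matching interval.
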